### 9.3.2 Missing Baseline Evaluation

Missing baseline will not be imputed.

### 9.3.3 Missing Post-Baseline Evaluation

Primary analysis of continuous efficacy endpoints will be analyzed based on observed data without imputation.

In the sensitivity analysis of primary and the secondary efficacy endpoints, missing continuous efficacy endpoints will be handled using the LOCF method.

In the LOCF method, post-baseline missing continuous endpoints will be imputed using the last observed value including baseline value. For example, if subject has all of the post-baseline values as missing, then all of the post-baseline values will be imputed using the observed baseline value.

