### **4.3 Subject Withdrawal**

Any subject is free to withdraw from participation in the study at any time, for any reason, specified or unspecified, and without prejudice to further treatment. The criteria for enrollment are to be followed explicitly. If a subject who does not meet enrollment criteria is inadvertently enrolled, that subject should be withdrawn from the study and the Sponsor/contract research organization (CRO) must be contacted. An exception may be granted in rare circumstances where there is a compelling reason to allow the subject to continue. In these rare cases, the investigator must obtain documented approval from the Sponsor or Sponsor designee to allow the subject to continue in the study.

In addition, subjects will be withdrawn from study drug and from the study in the following circumstances:

- The investigator decides that the subject should be withdrawn. If this decision is made because of an intolerable AE or a clinically significant laboratory value, if the dose of study drug has not been administered, it will be withheld and appropriate measures are to be taken. The Sponsor or Sponsor designee is to be notified immediately.
- The subject is unwilling to continue in the study.
- The subject is not compliant with the protocol.
- The investigator or the Sponsor, for any reason, stops the study.

If a subject prematurely withdraws from the study, every effort must be made to have the subject return to the clinical site for a premature termination visit. In all cases, the reason for withdrawal must be recorded in the Electronic Case Report Form (eCRF) and in the subject's medical records.

Contact will be maintained with subjects who are removed due to an AE until it has been resolved or stabilized, and the information will be documented in the eCRF and in the subject's medical records.

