At the same time, hyperglycemia will be well maintained by examining subjects bi-weekly. Taking Cyclo-Z may increase fasting blood glucose initially for 2 months due to the reduction in pancreatic insulin secretion, which could occur with improved insulin sensitivity. Subjects will be instructed to monitor for increased thirst, urination and blurry vision, but subjects will also be advised that the best method for detecting hyperglycemia is by measuring blood glucose level.

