## **5.9 Medication Accountability and Treatment Compliance**

Subjects will return all unused study medications with the diary at Visits 3, 4, 5, 6, 7, and 8 (Weeks 2, 4, 6, 8, 10, and 12) or at Early Termination Visit. The returned medications and diaries will be reviewed with the subject to evaluate the medication accountability and treatment compliance. If a subject misses 3 or more doses out of total 2-week doses (i.e., 14 doses), the site should contact the Sponsor for the discussion of potential early termination.

All study medication supplies should be accounted for at the termination of the study and a written explanation provided for discrepancies. All unused study medication supplies and packaging materials are

to be inventoried and returned to the Sponsor by the investigator. The investigator is not permitted to return or destroy unused clinical drug supplies or packaging materials unless authorized by the Sponsor.

The medication doses for the diabetes treatment should not be changed during the 3-month treatment period.

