#### 8.1.3 Primary Efficacy Analyses

The change from baseline to Week 12 in HbA1c will be compared for the experimental groups versus the control group using analysis of variance (ANOVA) methods if the change is approximately normally distributed. If the change is markedly non-normally distributed then Wilcoxon rank sum tests will be used. Specifically, all three experimental groups will be compared to the control group on the change: Dose A vs. D, B vs. D, and C vs. D.

The change from baseline to Week 12 in BW will be compared for the experimental groups versus the control group using ANOVA methods if the change is approximately normally distributed. If the change is markedly non-normally distributed then Wilcoxon rank sum tests will be used.

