### 8.1.8 Missing Data

No adjustments for missing data and no imputation methods are planned for this phase 2 study.

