If a subject experiences an increase in FPG level of >270 mg/dl from baseline to Week 6 or >240 mg/dl from Week 6 to 12, the subject will be instructed to take his/her own hypoglycemic agent. It is expected that glucose levels can be controlled in most diabetic subjects by these treatments. If the subject's blood glucose levels do not decrease to an acceptable level (<240 mg/dl) after 2 weeks, the subject will be referred to a diabetologist and will be terminated from the study. The study physician will continue to evaluate and treat the subject as needed until healthcare is turned over to the diabetologist.

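### The primary Week 12 test uses only observed Week 12 values, with no baseline term, although exits can depend on glucose; a repeated-measures model for HbA1c would reduce the possible bias but not remove it

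*SAP*

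**What the plan says.** SAP 9.3.3: "Primary analysis of continuous efficacy endpoints will be analyzed based on observed data without imputation". The table in SAP 10.5 and the text of 10.5.1 make the primary test a one-way ANOVA across the four groups, with Dunnett comparisons of A, B and C against D. Rank tests replace these if the changes are markedly non-normal. No baseline covariate is named. This follows the protocol. Section 8.1.3 says the HbA1c change "will be compared for the experimental groups versus the control group using analysis of variance (ANOVA) methods", and 8.1.8 says "No adjustments for missing data and no imputation methods are planned for this phase 2 study". The sensitivity analyses are LOCF in the Efficacy Analysis Set and a repeat in the Per Protocol Set, from which SAP 7.3 excludes anyone withdrawn or terminated early.

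On exits, Protocol 4.3 says "subjects will be withdrawn from study drug and from the study in the following circumstances", and non-compliance is on the list. Under Protocol 9.5, if glucose is not below 240 mg/dl two weeks after the hyperglycemia step, "the subject will be referred to a diabetologist and will be terminated from the study". Protocol 5.8 adds: "Taking Cyclo-Z may increase fasting blood glucose initially for 2 months due to the reduction in pancreatic insulin secretion". Other text points the other way. Protocol 9.5 says "It is expected that glucose levels can be controlled in most diabetic subjects by these treatments", and after three or more missed doses in a two-week supply, Protocol 5.9 says "the site should contact the Sponsor for the discussion of potential early termination", which is not automatic removal.

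SAP 9.4 maps an early-termination value to the nearest scheduled visit, decided case by case. HbA1c is collected at Weeks 0, 4, 8 and 12, and weight at every visit.

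**The concern.** A subject who leaves contributes to the Week 12 test only if the exit falls close enough to Week 12 for the last value to be mapped there. Otherwise the Week 4 and 8 HbA1c values and the two-weekly weights do not inform the primary test. If leavers have worse control than completers and the arms lose different shares, the completers' difference is biased. It moves toward no effect if placebo loses more poorly controlled subjects, and in the drug's favour if the active arms do. The protocol supplies a mechanism for each: effective treatment would spare active subjects from the glucose rule, while an early fasting glucose rise on drug would push them into it.

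The planned checks do not settle the matter. The Per Protocol Set removes the subjects in question, and LOCF freezes a leaver's value while the others may still be changing.

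**Working it through.** **What the documents supply.** There are 64 subjects, 16 per arm. No dropout rate, SD, effect size or power is given. The only loss figure is screening failure, and it reproduces: 64 / (1 − 0.20) = 80 screened. Everything below rests on assumed inputs.

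**Closed form.** Let p be an arm's exit share and D the leavers' minus completers' mean Week 12 change. The completers' mean equals the full mean minus pD. With the same D in both arms, the bias in active minus placebo is −(pA − pP) × D.
- Equal exits: 0.
- 10-point gap, D = 0.5: 0.10 × 0.5 = 0.05.
- 15-point gap, D = 1.0: 0.15.
- 20-point gap, D = 1.5: 0.30.

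The SE at 16 per arm is SD × √(2/16), which is 0.283, 0.354 and 0.424 for SDs of 0.8, 1.0 and 1.2. At SD 1.0, 0.15 is 0.42 SE and 0.30 is 0.85 SE.

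**Simulation A: exit driven by the HbA1c change at Week 4 or Week 8.** 1,000,000 per arm. Baseline SD 0.7, correlation −0.3 with changes. Change SD 0.6, 0.9 and 1.0 at Weeks 4, 8 and 12. Placebo removal 5, 10 or 20%. Arm shift in the trigger in line with the effect, zero, or +0.3 SD. True difference −0.75.

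| Exit after | Observed-case | Likelihood model with baseline | LOCF |
|---|---|---|---|
| Week 8 | −0.65 to −0.83 | −0.75 | −0.72 to −0.75 |
| Week 4 | −0.69 to −0.81 | −0.75 | −0.64 to −0.74 |

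At 5% placebo removal the observed-case bias is at most 0.04 (Week 8) or 0.03 (Week 4). With the same trigger in all arms it is zero. The model's exact recovery is built in, because this exit mechanism is missing at random given HbA1c. With a 0.2 loading on the Week 12 residual, observed-case gives −0.63 to −0.85 and the model −0.72 to −0.78.

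**Simulation B: exit driven by fasting glucose.** 400,000 per arm. The Protocol 9.5 thresholds are read as FPG levels (an assumption). Mean FPG 170 or 190 mg/dl, SD 40, SD of HbA1c change 0.8 to 1.2, plus 10% unrelated exits. Bias in HbA1c points; negative favours the drug:

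| Scenario | Observed-case | Model | LOCF |
|---|---|---|---|
| No effect, no FPG rise | 0.00 | 0.00 | 0.00 |
| Effect −0.5 | +0.012 to +0.049 | +0.005 to +0.022 | +0.031 to +0.048 |
| Effect −0.5, FPG +30 to Week 8 | −0.018 to −0.057 | −0.010 to −0.038 | +0.029 to +0.051 |
| No effect, FPG +30 | −0.041 to −0.127 | −0.020 to −0.072 | −0.012 to −0.029 |

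The largest observed-case value here is 0.127 / 0.424 = 0.30 SE. The model removes about one third to three fifths of the bias. In a stress case (FPG +50, 35 to 52% active exits) the observed-case bias is −0.086 to −0.237, up to 0.56 SE, and the model leaves up to −0.141.

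**Body weight.** 600,000 per arm, true −2.0 kg: observed-case −1.86 to −2.12, model −1.99 to −2.01, LOCF −1.60 to −1.99. The largest observed-case bias is 0.14 kg against a sampling SD of about 1.1 to 1.3 kg.

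**Error rates, four arms of 16.**
- HbA1c (3,000 trials per scenario): family-wise Dunnett error 4.1 to 5.2% observed-case, 3.9 to 4.6% for the model.
- Weight with exits (1,000 trials per scenario, Monte Carlo SE about 0.8 points): 6.4 to 7.4% for the model, against 5.4 to 6.4% observed-case in the same trials. The top value is (7.4 − 5) / 0.8 = 3 Monte Carlo SEs above nominal.

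**Precision.** HbA1c power for any dose (all at −0.75) was 62 to 67% for the model and 58 to 64% for observed-case. Baseline adjustment alone takes the SE from 0.354 to 0.354 × √(1 − 0.3²) = 0.337, so most of this gain is not due to the Week 4 and 8 data.

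**The case against.** Observed-case ANOVA is an explicit protocol choice in an unpowered exploratory trial. The plan already has an LOCF sensitivity analysis, an early-termination visit that measures HbA1c and weight, and tabulation of the timing of and reasons for withdrawal, so a reader can see unequal exits. Simulated harm under moderate rates is a fraction of a standard error, and the HbA1c error rate holds. LOCF was less biased than the model in the scenario with no effect and an early FPG rise. For weight, the model may inflate error to remove a bias of about 0.13 SE.

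Much of this stands. The choice is deliberate and the trial is not invalidated. The weight result is good reason not to make the model primary there. Neither LOCF nor the model is better in every scenario: LOCF was worse than the model where the drug worked without an early rise. What does not stand is that the present checks suffice. None makes principled use of the leavers' earlier values, and a withdrawal table shows imbalance without estimating its effect.

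A reader might also infer that the SAP contradicts itself on whether the primary test uses LOCF. The opening of SAP 9.3 and its counterpart in Section 13 do state LOCF without limit. But 9.3.3 is the specific rule, and the tables in 10.5 and 13 both put LOCF under sensitivity analysis. This is loose wording.

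**Conclusion.** The point holds as an inexpensive improvement to the HbA1c analysis. The primary test leaves out leavers' data and baseline, and exits could be related to outcome and unequal between arms. The bias is about 0.1 HbA1c points under moderate assumed rates (largest 0.13, or 0.30 SE). It is larger if exits differ by 15 to 20 points and leavers do 1.0 to 1.5 points worse than completers. Exit rates, SDs and glucose distributions are all assumed.

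Three stronger readings are not supported:
- **The result would be biased toward the drug.** Both directions follow from the protocol's own mechanisms, and equal exit triggers gave no bias.
- **The bias is known to be small.** That would need exit rates, and the documents give none.
- **A repeated-measures model would remove the bias.** The Protocol 9.5 trigger is fasting glucose, which an HbA1c-only model does not contain, so the bias is only reduced.

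**What to change.** 1. **HbA1c:** make the primary analysis a likelihood-based repeated-measures model on the Week 4, 8 and 12 changes, with treatment, visit, treatment-by-visit, baseline and baseline-by-visit terms and a Kenward-Roger correction. Name the covariance structure and its fallbacks in advance. Take from it the Week 12 four-group test and the Dunnett-adjusted contrasts of A, B and C with D. Keep the observed-case ANOVA/Dunnett and LOCF as sensitivity analyses.
2. **Body weight:** keep the planned ANOVA/Dunnett as primary and add the same model on Weeks 2 to 12 as a sensitivity analysis.
3. **Missing not at random:** add one sensitivity analysis that departs from missing at random, for example shifting leavers' Week 12 values by a range of amounts, separately by arm.
4. **Non-normality:** state that the rank tests in SAP 10.5.1 govern if the data are markedly non-normal.
5. **Record:** list the departure from Protocol 8.1.3 and 8.1.8 in SAP 13.
6. **Wording repair:** limit the LOCF sentences in SAP 9.3 and 13 to the sensitivity analysis. Choose one rule for a subject with no post-baseline value on an endpoint. SAP 9.3.3 carries baseline forward, while Section 13 asks for a post-baseline measurement. Because Efficacy Analysis Set entry already needs some post-baseline efficacy data, this conflict arises only endpoint by endpoint.

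The cost is SAP text, one mixed model per co-primary endpoint and one further sensitivity analysis, with no new visits or data. The downsides are reliance on missing at random and slightly more complexity, for a modest precision gain that comes mostly from baseline adjustment.

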3.1.2 Schedule of Assessment

Study Visits 	Screening	Treatment Period							Follow-up
	V1	V2	V3	V4	V5	V6	V7	V8	V9
	Screen (Week -2)	Baseline (Week 0)	Week 2	Week 4	Week 6	Week 8	Week 10	Week 12	Week 14
Informed Consent	X								
Inclusion/Exclusion Criteria	X	X							
Demographic (including height)	X								
Medical/Medication History	X								
Physical Examination	X	X		X		X		X	
Vital Signs and Body Weight	X	X	X	X	X	X	X	X	X
12-lead ECG	X							X	
Blood Sampling for serum chemistry, hematology, FPG, HbA1c, hCG, TSH, T3, and T4 	X	X		X		X		X	
Blood Sampling for zinc, insulin, adiponectin, C-peptide, leptin, glucagon, [CHP in a subset of subjects 		X		X		X		X	
Urine Sampling for glucose, microalbumin, copper, and zinc		X		X		X		X	
Dispense and Review Daily Log	X	X	X	X	X	X	X	X	
Dispense and Review Medications		X	X	X	X	X	X	X	
Waist Circumference		X		X		X		X	
OGTT 		X						X	
ADDQoL Questionnaire		X						X	
Review of Adverse Event and Concomitant Medication 		X	X	X	X	X	X	X	X

- 1) Visits 3 to 8 have ±3 day visit window and Visit 9 has +7 day visit window.
- 2) Serum chemistry, hematology: Weeks -2, 0, 4, 8, and 12  
HbA1c: Weeks -2, 0, 4, 8, and 12  
FPG: Weeks 0, 4, 8, and 12  
TSH, T3, T4: Weeks 0 and 12  
Serum hCG (pregnancy): Weeks -2 and 12
- 3) CHP levels may be analyzed in a subset of subjects if residual serum and/or plasma samples are available after completion of protocol-required tests.
- 4) Subjects will be advised to maintain similar exercise and eating habits 3 days prior to the OGTT. Each subject will be instructed not to take his or her usual oral medications or insulin injection and food at least 12 hours before coming to the clinical site between 7:00 am and 8:30 am for an OGTT. Each subject will be allowed to drink only water during the 12-hour fasting period prior to the OGTT and advised not to consume any food. Initial blood will be drawn (15 min prior to OGTT) for serum chemical analysis. The subject will then consume a glucose solution (75 g), followed by one drop of blood drawn for glucose measurements with a glucometer at 0, 0.5, 1.0, 1.5, 2.0, 2.5 and 3 h in the clinical site.
- 5) Assess hypoglycemic & hyperglycemic episodes at Visits 2 to 8 only.

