## 7.3 Per Protocol Set

All subjects valid for EAS who meet ALL the following criteria will be „valid per protocol“ (also called „valid for efficacy“):

- Complete at least 2 weeks of treatment after randomization.
- Have both baseline and at least 2 weeks of efficacy data.
- Subject did not have any significant violation after randomization.

Major protocol deviations that will potentially impact the primary analysis of efficacy endpoints at Week12 or violate GCP at site will be discussed and decided prior to the database lock and will be applied in per protocol analysis:

The following cases are excluded from the Per Protocol Set:

- Informed consent was not provided
- Subjects who were withdrawn/early terminated
- Subjects who have not met inclusion/exclusion criteria
- Subjects who received excluded concomitant medications
- Subjects who have major protocol deviations - all protocol deviations will be classified as major or minor under the discussion with Sponsor before database is locked.

Additional criteria maybe added prior to unblinding of the study database.

**The Per Protocol Set will be used to perform the sensitivity analysis on the primary, the secondary, and the exploratory efficacy endpoints.**

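### LOCF is the only planned Week 12 analysis that brings in early leavers, and its result may depend on exit time because the protocol allows for an early fasting-glucose rise on Cyclo-Z

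*SAP*

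**What the plan says.** SAP 9.3.3 sets the main rule: "Primary analysis of continuous efficacy endpoints will be analyzed based on observed data without imputation". A subject without a Week 12 value therefore drops out of the main comparison. The same section then gives the check: "In the sensitivity analysis of primary and the secondary efficacy endpoints, missing continuous efficacy endpoints will be handled using the LOCF method". The value carried may be the baseline value: "post-baseline missing continuous endpoints will be imputed using the last observed value including baseline value". SAP 10.5, 10.5.1 and 10.5.2 repeat LOCF as a sensitivity analysis for the primary and secondary endpoints.

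The other planned sensitivity analysis uses the Per Protocol Set, and SAP 7.3 lists among its exclusions "Subjects who were withdrawn/early terminated".

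The schedule in SAP 3.1.2 gives "HbA1c: Weeks -2, 0, 4, 8, and 12" and "FPG: Weeks 0, 4, 8, and 12". Body weight is taken at every visit. On timing it says "Visits 3 to 8 have ±3 day visit window and Visit 9 has +7 day visit window".

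Protocol 5.8 states: "Taking Cyclo-Z may increase fasting blood glucose initially for 2 months due to the reduction in pancreatic insulin secretion". It gives no size for the rise and does not mention HbA1c or body weight.

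**The concern.** LOCF treats the last value as the one the subject would have had at Week 12. The protocol allows for a different course on the active arms: fasting glucose that may be raised for about two months and then not. If that happens, a Cyclo-Z subject who leaves in that period has a temporary value entered as the Week 12 outcome. A placebo subject who leaves at the same time has no such drug effect in the carried value.

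The sensitivity analysis should show whether the Week 12 result survives missing data. If its answer moves with the day on which subjects leave, disagreement with the main result may only reflect exit times, and agreement says little about missing data. LOCF also counts a carried value as if it had been measured, so its standard errors take no account of the imputation.

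**Working it through.** The plan states no exit rate, effect size, standard deviation or size of the early rise, so there is no figure of its own to reproduce.

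**Which analyses include leavers.** The observed-data analysis excludes subjects with no Week 12 value. The Per Protocol analysis excludes early-terminated subjects. The outlier and post-hoc analyses (SAP 9.5, 10.8, 10.9) are optional and not aimed at leavers. Only LOCF remains.

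**Timing.** Week 4 is day 28 ± 3 = days 25 to 31. Week 8 is day 56 ± 3 = days 53 to 59. Two months is 365.25/6 = 60.9 days. Both visits fall inside it, Week 8 narrowly. If windows accumulate from visit to visit, as Protocol 6.2.2 and 6.2.3 can be read, Week 8 is 56 ± (4 × 3) = days 44 to 68.

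**Other donors.** Baseline may be carried. An early termination visit with HbA1c and FPG is also sought (Protocol 4.3, 6.2.4) and is mapped to the closest scheduled visit (SAP 9.4). An exit value after about day 61 lies outside the two months.

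**Illustration for FPG.** Assumptions:
- Week 12 effect -14.1 mg/dL, the midpoint (11.0 + 17.2)/2 of the range that Protocol 1.1 cites for a DPP-4 inhibitor.
- Exit share 16%, the treatment-arm figure that Protocol 1.1 cites for GLP-1.
- Exits even over 84 days, no placebo exits, placebo flat.
- Exits on days 1 to 60 carry a rise of r mg/dL (assumed).
- Exits on days 61 to 77 carry no benefit.
- Exits on days 78 to 84 are nearest to Week 12 and lose nothing.

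Effect removed = 0.16 × [(60/84) × (r + 14.1) + (17/84) × 14.1].

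| r (mg/dL) | Removed (mg/dL) | Share of 14.1 |
|---|---|---|
| 0 | 1.61 + 0.46 = 2.07 | 15% |
| 10 | 2.75 + 0.46 = 3.21 | 23% |
| 20 | 3.90 + 0.46 = 4.35 | 31% |
| 30 | 5.04 + 0.46 = 5.50 | 39% |

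The first 15% arises with no rise at all. The rise itself adds 0.16 × (60/84) × r / 14.1, which is 8 percentage points at r = 10 and 24 at r = 30. If the exits on days 61 to 77 carried the full benefit instead, the second term vanishes and the range for r = 10 to 30 is 20% to 36%.

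**Sign, for HbA1c.** Bias in the drug-minus-placebo change = leaver share × (carried change - target Week 12 change), with placebo flat. At an assumed 20% of leavers, in percentage points (positive = against the drug):

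| Assumed change at Weeks 4, 8, 12 | Target | Baseline carried | Week 4 carried | Week 8 carried |
|---|---|---|---|---|
| +0.2, +0.2, -0.5 | on treatment | +0.10 | +0.14 | +0.14 |
| -0.17, -0.33, -0.5 | on treatment | +0.10 | +0.07 | +0.03 |
| +0.2, +0.2, +0.2 | on treatment | -0.04 | 0 | 0 |
| -0.3, -0.5, -0.3 | on treatment | +0.06 | 0 | -0.04 |
| -0.17, -0.33, -0.5 | off drug, back at baseline | 0 | -0.03 | -0.07 |

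For scale, the standard error of a difference between two arms of 16 is SD × √(2/16) = 0.28, 0.35 or 0.42 for an assumed SD of 0.8, 1.0 or 1.2. Every bias in the table is smaller.

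**The case against.** A reader might infer that LOCF is biased against Cyclo-Z as a matter of fact. The documents do not support that. Protocol 5.8 describes a possibility without a size. The direction needs a rise that occurs, reverses by Week 12, and a target equal to the on-treatment Week 12 value. The SAP names no target for leavers. The second table shows zero or opposite bias under other courses or an off-drug target. The termination rule for persistently high glucose (Protocol 9.5) is not specific to any arm, so a placebo subject who leaves under it would carry a high value forward, which favours the drug.

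A reader might also apply the early rise to every exit, which gives 0.16 × (30 + 14.1)/14.1 = 50% at 30 mg/dL. That ignores exits after the two months, exits mapped to Week 12, and leavers whose baseline value is carried.

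Nor is shrinkage alone a fault: an analysis that gives leavers a placebo-like course shrinks the effect on purpose. LOCF is only supportive here, the trial is exploratory and not formally powered, by-visit summaries would show whether an early rise occurred, and withdrawal timing and reasons are to be tabulated or listed (SAP 9.6).

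All of this stands, and it limits direction, reach and size. It does not supply another Week 12 analysis that includes leavers, and it does not make a flat course a sound assumption. A carried value tied to no stated target, with an error that changes sign with course and exit day, is a weak test of robustness.

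**Conclusion.** The point holds in conditional form. LOCF is the only planned Week 12 analysis that includes subjects without a Week 12 value, and its scheduled FPG and HbA1c donors fall inside the period in which the protocol says fasting glucose may rise. Its result may depend on exit time, possibly against the drug. The link is direct for FPG, a secondary endpoint. For HbA1c it is an inference from fasting glucose. For body weight the protocol statement does not apply, and only the general objection to freezing a developing change remains.

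The 23% to 39% for FPG rests on an effect and exit rate borrowed from other drugs and on an assumed rise, and it shows scale only. The HbA1c biases examined are below one standard error of an arm difference, so they would distort the check rather than decide the trial.

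**What to change.** In SAP 9.3.3, 10.5, 10.5.1 and 10.5.2:

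- Make the main missing-data sensitivity analysis for HbA1c, body weight and FPG a likelihood-based repeated-measures model. It should use baseline and all observed post-baseline visits (Weeks 4, 8 and 12 for HbA1c and FPG; all treatment visits for body weight), with arm-by-visit terms, a covariance shared across arms, and each dose compared with placebo at Week 12.
- State the target for leavers, and say how an exit value that maps to a visit with no scheduled HbA1c or FPG enters the model.
- Add a tipping-point analysis for the two co-primary endpoints that shifts leavers' Week 12 values until the conclusion changes.
- Keep LOCF as description only. Bring the opening of SAP 9.3, which states LOCF without confining it to sensitivity analysis, into line with 9.3.3.

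A shared covariance is preferable to imputation fitted separately by arm: with 16 per arm, 16% exits means 0.16 × 16 = 2.6, or 2 to 3 leavers per arm. The cost is SAP wording and modest programming on data already collected. Intervals will be somewhat wider than under LOCF, and with so few leavers per arm the information about them stays limited.
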